1.1.5. Clinical Trials of Andecaliximab

Andecaliximab is being investigated for the treatment of solid tumors, inflammatory bowel disease, rheumatoid arthritis, cystic fibrosis, and chronic obstructive pulmonary disease. Brief summaries of the solid tumor clinical trials are provided herein.

Study GS-US-296-0101 is a Phase 1, open-label, sequential dose-escalation, and expansion study to evaluate safety, pharmacokinetics (PK), and pharmacodynamics of andecaliximab following multiple IV administrations of andecaliximab alone (at 200, 600, and 1800 mg every 2 weeks [Q2W]) or in combination with chemotherapy (at 800 mg Q2W or 1200 mg every 3 weeks [Q3W]) in subjects with advanced solid tumors.

As of January 12, 2016, Study GS-US-296-0101 had enrolled 40 subjects with metastatic gastric adenocarcinoma (14 remain on study). Grade 3 or higher treatment-emergent AEs (TEAEs) included neutropenia (18%), nausea (10%), and neutrophil count decreased (10%). The most common serious TEAEs were abdominal pain, GI hemorrhage, hyponatremia, nausea, pyrexia, and septic shock each occurring in 2 subjects (5%). Median progression free survival (PFS) for all 40 subjects was 7.4 months (90% confidence interval (CI) = [5.0, 12.5]), with a median duration of response (DOR) of 9.4 months and an objective response rate (ORR) of 50%. Of those subjects, 30 were chemotherapy naïve (eg, first-line), and demonstrated a median PFS of 12.0 (90% CI = [5.5, 18.0]) months, with a median DOR of 10.6 months and an ORR of 57%. Collagen neopeptide decreased with continued treatment, demonstrating on-target effects.

This efficacy data combined with the favorable safety profile continues to support evaluation of andecaliximab in a Phase 3 study of this fatal disease where therapeutic options are limited and non-curative.

Study GS-US-296-1080 is a Phase 3, randomized, double-blind, placebo-controlled study to evaluate the efficacy and safety of andecaliximab in combination with mFOLFOX6 as first-line treatment in subjects with advanced gastric or GEJ adenocarcinoma. A dose of 800 mg Q2W in combination with mFOLFOX6 is being evaluated globally at centers in the United States, Europe, Latin America, and Australia.

Study GS US-296-1884 is a Phase 1b clinical study of Japanese subjects to evaluate safety and tolerability of GS5745 as monotherapy and in combination with chemotherapy.

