5.4.2. Prohibited Concomitant Medications

Subjects are prohibited from receiving the following therapies during the Screening and Treatment Phase (including retreatment for post-complete response relapse) of this trial:

- Antineoplastic chemotherapy or biological therapy not specified in the protocol
- Immunotherapy not specified in this protocol
- Investigational agents other than those specified by the protocol

- Radiation therapy
 - Note: Radiation therapy to a symptomatic solitary lesion or to the brain may be considered on an exceptional case-by-case basis after consultation with the Sponsor. The subject must have clear measurable disease outside the radiated field. Administration of palliative radiation therapy will be considered clinical progression for the purposes of determining PFS.
- Live vaccines within 30 days prior to the first dose of trial treatment and while participating in the trial. Examples of live vaccines include, but are not limited to, the following: measles, mumps, rubella, chicken pox, yellow fever, rabies, BCG, and typhoid (oral) vaccine. Seasonal influenza vaccines for injection are generally killed virus vaccines and are allowed. However, intranasal influenza vaccines (eg, Flu - Mist®) are live attenuated vaccines, and are not allowed.
- Systemic glucocorticoids for any purpose other than to modulate symptoms from an event of suspected immunologic etiology. The use of physiologic doses of corticosteroids may be approved after consultation with the Sponsor.
 - Note: Inhaled steroids are allowed for management of asthma.

Subjects who, in the assessment by the investigator, require the use of any of the aforementioned treatments for clinical management should be removed from the trial. Subjects may receive other medications that the investigator deems to be medically necessary.

The Exclusion Criteria describes other medications that are prohibited in this trial.

There are no prohibited therapies during the Post-Treatment Follow-up Phase.

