8.2.1.2. Safety Analysis Set

The Safety Analysis Set will include data from all subjects who receive ≥ 1 dose of study treatment, with treatment assignments designated according to the actual treatment received.

This analysis set will be used in the analysis of safety variables as well as study treatment administration. All data collected up to 30 days after the last dose of andecaliximab or 5 months post-treatment of nivolumab, whichever is later, will be included in the safety summaries.

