8.6. Safety Analysis

All safety data collected on or after the date that andecaliximab/nivolumab was first administered up to 30 days after the last dose of andecaliximab or 5 months post-treatment of nivolumab, whichever is later, will be summarized by treatment group (according to the treatment received). Data for the pre-treatment and post-treatment follow-up period will be included in data listings.

In general, count and percent of subjects will summarize categorical and ordinal data. Mean, standard deviation, minimum, quartiles, median, and maximum will summarize continuous data.

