6.1. Primary Efficacy Endpoint

The primary efficacy endpoint of this study is objective response rate (ORR), defined as the proportion of subjects with best overall response of complete response (CR) or partial response (PR) after starting study drug but before starting any new chemotherapy or radiotherapy based on revised RECIST 1.1.

As sensitivity analysis, confirmed ORR, defined as the proportion of subjects with best overall response of confirmed CR or confirmed partial response (PR) after starting study drug but before starting any new anti-cancer therapy based on revised RECIST 1.1, will also be analyzed. The confirmatory response is required at least 4-week later after the initial CR/PR for confirmed ORR.

Overall response for each visit is derived in the following process. The rules should be applied by the order listed below.

- Response assessments occurring after new anticancer therapy (including radiation therapy), after missing two previous consecutive tumor scans, or after confirmed progressive disease (PD) will not be included for ORR analysis.
- If overall response for the first time point of a visit is an imaging PD, in order to differentiate “pseudo-progression (pseudo-PD)” from “definitive progression”, the first imaging PD requires confirmation either by another imaging PD at the confirmatory visit at least 4 weeks apart or by the subsequent clinical PD/ radiation therapy. The first imaging PD will be considered as “confirmed PD” by any of the following:
 - The overall response at the confirmatory visit is also PD;
 - No more tumor assessment is available that is 4 weeks apart;
 - The overall response at the confirmatory visit is non-evaluable (NE) and no more tumor assessments follow the confirmatory visit;
 - First imaging PD is followed by subsequent clinical PD or radiation therapy.

Otherwise, the first imaging PD will be “Pseudo PD”.

- Both clinical PD and radiation therapy are considered as PD, and no confirmation is required.

The best overall response for each subject across the time points is derived based on the rank CR > PR > SD > pseudo-PD > PD (including clinical PD, confirmed imaging PD, and radiation therapy) > NE.

For confirmed overall response for each visit, in addition to the rules listed above, the following rules should also be applied.

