7.1.5. Treatment-Emergent Adverse Events

7.1.5.1. Definition of Treatment-Emergent Adverse Events

Treatment-emergent adverse events (TEAEs) are defined as both of the following:

- Any AEs with an onset date on or after the study drug start date and up to 30 days after permanent discontinuation of andecaliximab or 5 months after permanent discontinuation of nivolumab
- Any AEs leading to premature discontinuation of andecaliximab or nivolumab

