7.2. Laboratory Evaluations

Laboratory data collected during the study will be analyzed using qualitative methods. Shift from baseline to worst post-baseline assessment and Grade 3 or higher lab abnormalities will be summarized for the Safety Analysis Set and will include data collected up to the last dose of andecaliximab plus 30 days for subjects who have permanently discontinued andecaliximab or up to the last dose of nivolumab plus 5 months for subjects who have permanently discontinued nivolumab. Severity grade for lab abnormalities are defined by CTCAE 4.03.

Only central lab results will be used in the analyses.

A by-subject listing for laboratory test results will be provided by subject ID number and time point in chronological order for hematology, serum chemistry, urinalysis, coagulation, and thyroid function separately. Values falling outside of the relevant reference range and/or having a severity grade of 1 or higher on the CTCAE severity grade will be flagged in the data listings, as appropriate.

No formal statistical testing is planned.

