7.2.1.1. Treatment-Emergent Laboratory Abnormalities

Treatment-emergent laboratory abnormalities are defined as values that increase at least 1 toxicity grade from baseline at any postbaseline time point, up to and including the date of last dose of andecaliximab plus 30 days or nivolumab plus 5 months for subjects who permanently discontinued study drug, or the last available date in the database snapshot for subjects who were still on treatment at the time of an interim analysis. If the relevant baseline laboratory value is missing, any abnormality of at least Grade 1 observed within the time frame specified above will be considered treatment emergent.

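### Treatment-emergent AE and laboratory tables run to 5 months after nivolumab with no cut or flag at new anticancer therapy, so next-line toxicity can enter the all-cause safety comparison

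*SAP*

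**What the plan says.** - **Adverse events.** Under SAP 7.1.5.1 the window opens at first dose and closes "up to 30 days after permanent discontinuation of andecaliximab or 5 months after permanent discontinuation of nivolumab". Cause plays no part in the definition.
- **Laboratory values.** SAP 7.2.1.1 counts a rise of at least one grade "up to and including the date of last dose of andecaliximab plus 30 days or nivolumab plus 5 months for subjects who permanently discontinued". The shift and Grade 3 or higher summaries in SAP 7.2 run "up to the last dose of nivolumab plus 5 months for subjects who have permanently discontinued nivolumab" and use central laboratory results only.
- **Which limit governs.** Protocol 8.6 summarises safety data "up to 30 days after the last dose of andecaliximab or 5 months post-treatment of nivolumab, whichever is later"; Protocol 8.2.1.2 agrees, and SAP Tables 1 to 3 take the maximum of the two dates. Under Protocol 3.5.1 andecaliximab stops permanently no later than nivolumab, so nivolumab plus 5 months is the limit in both arms.
- **Other therapy in the window.** Protocol 5.4.2 states: "There are no prohibited therapies during the Post-Treatment Follow-up Phase". Protocol 6.9 records later anticancer therapy. SAP 5.4 shows post-treatment chemotherapy only as a by-subject listing, and the concomitant medication summary in SAP 7.4.2 leaves out drugs started after the last study dose.
- **Efficacy.** SAP 6.1 removes from ORR "Response assessments occurring after new anticancer therapy (including radiation therapy), after missing two previous consecutive tumor scans". SAP 6.2.1 censors PFS when new therapy other than radiation precedes definitive progression, and SAP 6.2.3 applies the same censoring to DOR.
- **Attribution.** SAP 7.1.6 also tabulates treatment-related AEs. Under SAP 7.1.3 these follow the investigator, and a missing relationship counts as related.

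**The concern.** Comparing safety between arms is a secondary objective (Protocol 2), and SAP 1 makes this SAP the basis of the clinical study report for everything except efficacy. Early switching is plausible. In the nivolumab reference study in Protocol 1.2, 7 of 58 subjects responded and 12 had stable disease, which leaves 39 of 58 (67%) with neither. The first on-study scan is at Week 8. A subject who stops then and starts another regimen could spend much of the treatment-emergent window on that regimen.

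Events caused by the later regimen would sit in the same rows as events on study drug, and no planned table would separate them. If one arm moves to next-line therapy sooner or more often, it picks up more such events. If both arms move equally, the same added events make a true difference look smaller.

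**Working it through.** The plan gives no figure on this point to reproduce. The check has two parts: which outputs are exposed, and how large the effect could be.

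**Window length.** With the SAP's own month of 30.4375 days, 5 × 30.4375 = 152.2 days. That is 152.2 / 30 = 5.1 times a 30-day window, or 122.2 days more per subject. The nominal length is the same in both arms, so arm bias needs a difference in uptake, timing or toxicity of next-line therapy.

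**Which outputs can take in next-line events**

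| Output | Filter on cause | Cut at new therapy | Exposed |
|---|---|---|---|
| All-cause TEAE, Grade 3+, SAE, fatal TEAE (SAP 7.1.6) | None | None | Yes |
| Deaths (SAP 7.1.6) | Split by AE, progression, other | None | Yes, partly separable |
| Treatment-related AEs and SAEs (SAP 7.1.6) | Investigator; blank counts as related | None | Only if judged related or blank |
| Graded laboratory abnormalities (SAP 7.2.1.2) | None; central results only | None | Yes, to a smaller extent |
| ORR, PFS, DOR (SAP 6.1, 6.2) | Not applicable | Yes | No |

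The laboratory exposure is smaller because, after treatment, hematology and chemistry are scheduled only at EOT, EOS, 30 days and 5 months (Protocol 6.2.8). The 5-month visit has a window of ±7 days, so a draw taken after the exact 5-month date falls outside the SAP limit. Low counts measured at a local laboratory are not analysed.

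**Size.** Inputs:
- p, background rate of a Grade 3 or higher event: 17%, from Protocol 1.3. That figure is for treatment-related Grade 3 or 4 events on nivolumab, so it is a placeholder for an all-cause rate. 40% is a second, assumed value.
- u, share of an arm starting next-line therapy inside the window: assumed.
- q, chance of a Grade 3 or higher event on that therapy inside the window: assumed, 20% to 60%.
- 60 subjects per arm (Protocol 3.2).

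With background and next-line events independent, the observed rate is 1 − (1 − p)(1 − u·q). With the same p in both arms, the false difference is (1 − p)·q·(uA − uB).

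At p = 17%, with 30% uptake in one arm and 50% in the other:
- q = 20%: 1 − 0.83 × 0.94 = 22.0% against 1 − 0.83 × 0.90 = 25.3%; difference 3.3 points.
- q = 60%: 1 − 0.83 × 0.82 = 31.9% against 1 − 0.83 × 0.70 = 41.9%; difference 10.0 points.

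| p | Uptake | q = 20% | q = 60% |
|---|---|---|---|
| 17% | 30% vs 50% | 3.3 | 10.0 |
| 17% | 20% vs 50% | 5.0 | 14.9 |
| 40% | 30% vs 50% | 2.4 | 7.2 |
| Either | Equal | 0 | 0 |

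The false difference always counts against the arm with more next-line therapy.

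**Equal uptake.** A true risk difference is multiplied by 1 − u·q. For u and q between 20% and 60% this runs from 1 − 0.04 = 0.96 to 1 − 0.36 = 0.64.

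**Against sampling error.** At q = 20% the standard error of the difference is √[(0.220 × 0.780 + 0.253 × 0.747)/60] = 7.8 points. At q = 60% it is √[(0.319 × 0.681 + 0.419 × 0.581)/60] = 8.8 points. The false differences are 3.3/7.8 = 0.4 and 10.0/8.8 = 1.1 standard errors.

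**The case against.** **Attribution.** A reader might infer that the plan books next-line toxicity as study-drug toxicity. It does not. The exposed AE tables are all-cause, and the treatment-related tables follow the investigator. This stands: the exact statement is that such events count as treatment-emergent.

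**Direction.** A reader might infer that the combination will look safer than it is, because delayed progression would hold back next-line therapy in Arm A. That presumes an efficacy result. If the combination fails sooner, the bias reverses, and the documents cannot say which.

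**Size.** No document gives an uptake rate. Protocol 1.3 notes that many patients are not fit for further chemotherapy, which points to lower uptake. The 18% Grade 3 or higher neutropenia in Protocol 1.1.5 is no substitute for a next-line rate: 30 of those 40 subjects were chemotherapy-naive. The illustrated effects are also modest beside sampling error with 60 per arm. All of this stands. The figures are a scale, not an estimate.

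**Window.** Protocol 8.6.2 ends TEAEs 30 days after permanent discontinuation. If that governed, therapy started more than 30 days after the last dose would add nothing to the TEAE tables, apart from AEs that led to stopping study drug. Footnote d of the study procedures table ends AE recording at the later of the 30-day and EOS visits, which could leave later events incompletely captured. This limits the point but does not remove it: the SAP as written applies 5 months, Protocol 6.2.11 and 7.3.1 collect to 5 months, and SAP 7.7 declares no change from the protocol.

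**Remedy.** Cutting at new therapy shortens observation more in the arm that switches sooner and drops delayed study-drug events. This stands, and it rules out resting the comparison on the cut tables alone.

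**Listings.** AEs and post-treatment chemotherapy can be matched by hand across two listings. That permits case review but does not give a comparison by arm.

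**Conclusion.** The point holds in a limited form. SAP 7.1.5.1 and 7.2.1.1 carry all-cause AEs and central laboratory abnormalities to 5 months after nivolumab and ignore the start of new anticancer therapy, which the same SAP takes into account for ORR, PFS and DOR. The exposed outputs are the all-cause TEAE, Grade 3 or higher, SAE and death tables and, less so, the laboratory tables.

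Under the assumed 17% background, 30% versus 50% uptake and 20% to 60% next-line event risk, the false arm difference is 3.3 to 10.0 points. With equal uptake it is zero, but a true difference shrinks to between 0.96 and 0.64 of its size over the range shown. Uptake and next-line risk are assumptions throughout. The documents do not support a stated direction of bias. The efficacy analyses are unaffected. This is a low-cost improvement to the reading of a secondary objective.

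**What to change.** Leave the 5-month tables unchanged, since they protect detection of late events. Then:

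1. In SAP 7.1.6, add by arm a second version of the overall AE summary and of the Grade 3 or higher, SAE and fatal TEAE tables. In SAP 7.2.1.2, do the same for the Grade 3 or 4 laboratory table. Count only onset before the earlier of the end of the safety window and the start of any new anticancer therapy.
2. Add exposure-adjusted rates to the second set (subjects with an event divided by total time at risk to first event or cut), because the cut shortens follow-up unequally.
3. Flag events with onset after the start of new therapy in the AE and laboratory listings.
4. Show both sets side by side, and do not rest the tolerability conclusion on the cut set alone.
5. Separately, reconcile the 30-day TEAE definition in Protocol 8.6.2 and footnote d of the study procedures table with the 5-month window in the SAP and in Protocol 6.2.11, 7.3.1 and 8.6.

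The cost of the added analyses is a few tables and no new data collection: later anticancer therapy is already recorded (Protocol 6.9, SAP 5.4). Study-drug events that appear after a switch will be absent from the cut set, though they stay in the full one. Partial therapy dates need imputation. SAP 6.2.1 already has a rule, but it moves a missing day to the end of the month, so the cut can fall up to about a month late and leave some next-line events in.

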7.1.5.2. Incomplete Dates

If the onset date of the AE is incomplete and the AE stop date is not prior to the first dosing date of study drug, then the month and year (or year alone if month is not recorded) of onset determine whether an AE is treatment emergent. The event is considered treatment emergent if both of the following 2 criteria are met:

- The AE onset is the same as or after the month and year (or year) of the first dosing date of study drug, and
- The AE onset date is the same as or before the month and year (or year) of the date corresponding to 30 days after the date of the last dose of andecaliximab or 5 months after the date of the last dose of nivolumab

An AE with completely missing onset and stop dates, or with the onset date missing and a stop date later than the first dosing date of study drug, will be considered to be treatment emergent. In addition, an AE with the onset date missing and incomplete stop date with the same or later month and year (or year alone if month is not recorded) as the first dosing date of study drug will be considered treatment emergent.

7.1.6. Summaries of Adverse Events and Deaths

Treatment-emergent AEs will be summarized based on the Safety Analysis Set.

The number and percentage of subjects who experienced at least 1 TEAE will be provided and summarized by SOC, HLT, PT, and treatment group. For other AEs described below, summaries will be provided by SOC, PT, and treatment group:

- All TE treatment-related AEs
- TEAEs of Grade 3 or higher (by maximum severity)
- TE Treatment-related AEs of Grade 3 or higher (by maximum severity)
- All TE SAEs
- All TE treatment-related SAEs
- All TEAEs leading to discontinuation of any study drug
- All TEAEs leading to study treatment interruption or dose interruption
- All TEAEs leading to death

A brief, high-level summary of AEs described above will be provided by treatment group and by the number and percentage of subjects who experienced the above AEs.

Multiple events will be counted only once per subject in each summary. Adverse events will be summarized and listed first in alphabetic order of SOC and HLT within each SOC, and then by PT in descending order of total frequency within each SOC. For summaries by severity grade, the most severe grade will be used for those AEs that occurred more than once in an individual subject during the study.

In addition to the above summary tables, all TEAEs and TE treatment-related AEs will be summarized by PT only, in descending order of total frequency.

Deaths will be summarized by whether it is considered treatment emergent and the cause of the death (AE, due to PD, or other reasons).

In addition, data listings will be provided for the following:

- All AEs, indicating whether the event is treatment emergent
- AEs with Grade 3 or higher
- SAEs
- AEs leading to death
- All deaths
- AEs leading to discontinuation of study drug
- AEs leading to treatment interruption/dose modification

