- Arm A: andecaliximab + nivolumab
- Arm B: nivolumab

Randomization and Stratification:

- 1:1 allocation to andecaliximab + nivolumab versus nivolumab alone through an interactive web response system (IWRS)
- Fixed-block centralized randomization stratified by:
 - PD-L1 positive versus PD-L1 negative

Number of
Subjects Planned:

Approximately 120 subjects

Target Population:	Subjects who are ≥ 18 years or older with a histologically confirmed inoperable locally advanced or metastatic adenocarcinoma of the stomach or the gastroesophageal junction (GEJ) and who have progressed on at least 1 prior systemic therapy or line of treatment for unresectable/metastatic disease
Duration of Treatment:	Treatment will be given every 2 weeks and will continue until disease progression, unacceptable toxicity, or withdrawal of consent to a maximum of 2 years duration
Eligibility Criteria:	
Inclusion Criteria
 
Subjects must meet all of the following inclusion criteria to be eligible for participation in this study:
 
1) Age ≥ 18 years2) Histologically confirmed inoperable locally advanced or metastatic adenocarcinoma of the stomach or GEJ which have progressed on at least 1 prior systemic therapy or line of treatment for unresectable/metastatic disease3) Eastern Cooperative Oncology Group (ECOG) ≤ 14) Measurable disease according to RECIST v1.15) Tumor sites that can be accessed for repeat biopsies6) Archival tumor tissue, preferably obtained from the most recent available biopsy; there must be adequate tissue for a PD-L1 stratification test, as assessed by central pathologist7) All toxicities attributed to prior anti-cancer therapy other than alopecia and fatigue must have resolved to Grade 1 (NCI CTCAE version 4) or baseline8) Subjects not receiving anticoagulant medication must have an international normalized ratio (INR) ≤ 1.5 and activated partial thromboplastin (aPTT) $\leq 1.5 \times$ upper limit of normal (ULN) prior to randomization. The use of full-dose oral or parenteral anticoagulants is permitted as long as the INR or aPTT is within therapeutic limits (according to the medical standard in the institution) and the subject has been on a stable dose of anticoagulants for at least 1 week at the time of randomization9) Adequate hematologic function
a) neutrophils $\geq 1.5 \times 10^9/L$b) platelets $\geq 100 \times 10^9/L$c) hemoglobin ≥ 9 g/dL

- 10) Adequate hepatic function

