3.4. Duration of Treatment

Starting on Day 1, treatment will be given every 2 weeks and will continue in the absence of disease progression or unacceptable toxicity, consent withdrawal or subject's refusal of treatment, or up to 2 years. There will be a screening period of up to 28 days. Following completion of treatment, subjects will be followed for safety at 30 days after last dose of andecaliximab and 5 months post-treatment of nivolumab, and for survival status approximately every 3 months for up to 5 years total.

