8.6.2. Adverse Events

Clinical and laboratory adverse events will be coded using the Medical Dictionary for Regulatory Activities (MedDRA). System Organ Class (SOC), High-Level Group Term (HLGT), High-Level Term (HLT), Preferred Term (PT), and Lower-Level Term (LLT) will be attached to the clinical database.

Events will be summarized on the basis of the date of onset for the event. A treatment-emergent AE is defined as any AE with onset date on or after the date of first dose of study drug up to 30 days after permanent study drug discontinuation or any adverse events leading to premature study drug discontinuation.

Summaries (number and percentage of subjects) of treatment-emergent AEs (by SOC and PT) will be provided by treatment group

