1.1. Study Objectives

The primary objective of this study is as follows:

- To evaluate and compare the efficacy of andecaliximab (GS-5745) in combination with nivolumab versus nivolumab alone in subjects with recurrent gastric or gastroesophageal junction (GEJ) adenocarcinoma

The secondary objectives of this study are as follows:

- To characterize and compare safety and tolerability of andecaliximab (GS-5745) in combination with nivolumab versus nivolumab alone in subjects with recurrent gastric or GEJ adenocarcinoma
- To characterize the pharmacokinetics (PK) of andecaliximab (GS-5745) in combination with nivolumab

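### Adverse events are compared between arms only as crude percentages of subjects, which misleads if the arms differ in time on treatment; exposure-adjusted rates would be a cheap addition

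*SAP*

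**What the plan says.** Comparing safety between arms is a secondary objective: "To characterize and compare safety and tolerability of andecaliximab (GS-5745) in combination with nivolumab versus nivolumab alone" (SAP 1.1; Protocol 2 agrees).

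The planned AE measure is in SAP 7.1.6: "The number and percentage of subjects who experienced at least 1 TEAE will be provided and summarized by SOC, HLT, PT, and treatment group". The counting rule there is "Multiple events will be counted only once per subject in each summary". The related, Grade 3 or higher, serious, discontinuation, interruption and death tables take the same form, as do the graded laboratory abnormalities in SAP 7.2.1.2. Protocol 8.3 adds 95% CIs on percentages. Neither document plans a rate per unit of time, a time-to-first-event analysis or a cumulative incidence for AEs.

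Time at risk is not fixed. The Protocol synopsis says that treatment "will continue until disease progression, unacceptable toxicity, or withdrawal of consent to a maximum of 2 years duration", and Protocol 3.4 says much the same. SAP 7.1.5.1 counts treatment-emergent AEs (TEAEs) "up to 30 days after permanent discontinuation of andecaliximab or 5 months after permanent discontinuation of nivolumab".

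Duration of exposure is summarized by arm (SAP 4.2.1), but it is not linked to the AE tables. SAP 1 makes this SAP the basis of the synoptic study report for everything except efficacy, so these tables will be the reported safety comparison.

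**The concern.** A percentage of subjects with at least one event depends on both the event rate and the length of observation. Here the length of observation is partly an efficacy outcome, because treatment stops at progression. If the combination delays progression, Arm A accrues more time at risk, and its percentages rise with no change in rate. If the combination does worse and is stopped sooner, the percentages hide some of its toxicity. Either way the tolerability comparison is mixed up with the efficacy result.

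The exposure table would reveal an imbalance. It would not let a reader correct the AE percentages, because the time to each subject's first event is not in it.

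**Working it through.** **The plan's own figure.** The documents give no calculated figure for safety. The only design figure is about 83% power for an objective response rate (ORR) of 25% versus 45%, at 60 per arm and one-sided 10%. A Wald test on the log odds ratio reproduces it:
- ln[(0.45/0.55)/(0.25/0.75)] = 0.898
- SE = √[1/(60×0.25×0.75) + 1/(60×0.45×0.55)] = 0.395
- Φ(0.898/0.395 − 1.282) ≈ 0.84 (83.9% unrounded)

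Nothing below depends on it.

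**Inputs.**
- From the documents: the 2-year cap on treatment; a follow-up window of L = 5 months after nivolumab, which both arms receive; 60 subjects per arm; ORR 25% and 45%; a median response duration of 7.1 months (95% CI 3.0–13.2) in the nivolumab study described in Protocol 1.2.
- Assumed, because the documents give neither: median time on treatment of 2 vs 3, 2 vs 4, 3 vs 4 or 3 vs 6 months (B vs A), and a constant AE hazard λ of 0.02 to 0.5 per month, the same in both arms.

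**Check 1: treatment time varies between subjects.** Let treatment time be exponential with rate θ = ln 2/median, capped at 24 months. Then

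crude % = 1 − e^(−λL) × [θ/(θ+λ) × (1 − e^(−24(θ+λ))) + e^(−24(θ+λ))].

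For λ = 0.10 and medians of 2 vs 4 months, e^(−0.5) = 0.6065:
- Arm B: θ = 0.3466, bracket = 0.7761, crude = 1 − 0.6065 × 0.7761 = 52.9%
- Arm A: θ = 0.1733, bracket = 0.6346, crude = 1 − 0.6065 × 0.6346 = 61.5%

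That is a false difference of 8.6 points. First events divided by time at risk give λ in both arms, 0.10 × 12 × 100 = 120 per 100 subject-years, a ratio of 1.00.

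| Case, 5-month window | Arm B | Arm A | Difference |
|---|---|---|---|
| 2 vs 4 months, λ 0.10 | 52.9% | 61.5% | +8.6 |
| 3 vs 6 months, λ 0.10 (largest) | 57.7% | 67.3% | +9.7 |
| 2 vs 4 months, λ 0.5 | 96.6% | 97.9% | +1.3 |
| 3 vs 4 months, λ 0.5 (smallest) | 97.4% | 97.9% | +0.5 |
| Equal medians, any λ | – | – | 0 |

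Two sensitivities:
- Allowing deaths in the follow-up window (assumed median 4 months), 2 vs 4 months at λ = 0.10 gives 43.5% vs 53.8% (+10.3). The largest value on the grid becomes +11.6.
- With a 30-day window, taken as 1 month, the same case gives 29.8% vs 42.6% (+12.8), and the grid runs from 2.3 to 14.4. The long common tail therefore dilutes the imbalance; the bias comes from time on treatment.

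**Check 2: only the extra responders stay on longer.** Assume 7 months at risk for non-responders (2 on treatment + 5) and 7.1 more for responders. Responders are 25% of Arm B and 45% of Arm A, so the difference is 0.20 × (e^(−7h) − e^(−14.1h)).
- Arm B at 30%: h = 0.0415, 0.20 × (0.748 − 0.557) = 0.038, so Arm A shows 33.8%.
- Arm B at 40%: h = 0.0600, 0.20 × (0.657 − 0.429) = 0.046, so Arm A shows 44.6%.
- The maximum over all h is about 5 points. With 13.2 extra months (the upper confidence limit), the two cases give 5.9 and 7.0 points.

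**Scale.** The 95% half-width of a difference at 60 per arm is 1.96 × √(2p(1−p)/60): 16.4 points at p = 0.3 and 17.9 at p = 0.5.

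**Which window.** The person-time denominator needs one window, and the documents disagree:
- Protocol 8.6.2: "up to 30 days after permanent study drug discontinuation or any adverse events leading to premature study drug discontinuation".
- SAP 7.1.5.1: up to 5 months after nivolumab, as quoted above.
- Protocol 8.2.1.2, for data in the safety summaries: "up to 30 days after the last dose of andecaliximab or 5 months post-treatment of nivolumab, whichever is later".
- Footnote d of the schedule (Protocol Appendix 2 and SAP Appendix 2): AE recording ends at the later of the 30-day visit and the end-of-study visit, although the table itself marks AEs at the 5-month visit.
- SAP 7.7: no deviation from the protocol's safety analyses.

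**The case against.** The best defence is that crude incidence with a separate exposure table is a coherent descriptive plan for a proof-of-concept study. Duration of exposure, number of doses and adherence are tabulated, and all AEs are listed. No hypothesis test on AEs is specified, so no error rate or decision rule changes. The bias is smaller than the sampling error. All of that stands, and it is why this is an improvement and not a defect that threatens the trial. It does not remove the point: the distortion is systematic, the planned confidence intervals do not reflect it, and the exposure table cannot be used to undo it.

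Three stronger readings are tempting, and the documents do not support them.
- A reader might infer false differences of 7 to 12 points. Putting every Arm B subject at 7 months at risk and every Arm A subject at 9 or 10 turns 30% into 36.8% or 39.9%, and 40% into 48.1% or 51.8%. The arithmetic is right, but the documents give no time on treatment. A 20-point gain in response does not imply 2 to 3 more months for everyone. Nor does it allow for deaths, although Protocol 1.2 cites survival of 6.8 months on nivolumab.
- A reader might infer that the combination will look more toxic. That follows only if Arm A is in fact treated longer. Treatment also ends for toxicity, withdrawal or the 2-year cap, and may continue past a first radiologic progression (Protocol 6.2.9.1).
- A reader might infer that all of the safety analysis is crude percentages. SAP 7.3 analyses vital signs and weight by visit, and Protocol 8.6.3 does so for laboratory data. The point concerns AEs and graded laboratory abnormalities.

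**Conclusion.** The point holds as a low-cost improvement. A planned between-arm comparison of AEs rests on percentages that take no account of time at risk, in a trial where time at risk depends partly on progression. The bias is conditional: against the longer-treated arm, zero if durations are equal, and in Arm A's favour if Arm A stops earlier.

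With the SAP's 5-month window the false difference is roughly 0.5 to 10 points (somewhat more if early deaths are allowed for), and about 4 to 5 points under the responder-only scenario. These figures rest on assumed treatment durations and equal, constant hazards, so they show the order of magnitude and do not predict the result. The consequence is for interpretation only.

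**What to change.** First reconcile the TEAE window across Protocol 8.6.2, SAP 7.1.5.1, footnote d of the schedule and the no-deviation statement in SAP 7.7.

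Then keep the percentages and add to SAP 7.1.6:
- **Rows:** any TEAE, Grade 3 or higher, serious, treatment-related, leading to discontinuation, and the most frequent preferred terms.
- **Measure:** subjects with a first event per 100 subject-years by arm, with the between-arm difference and its 95% CI.
- **Person-time:** from first dose to the earliest of first event, death, last contact, data cutoff or end of the agreed window.
- **Display:** total time at risk by arm beside the rates.

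The cost is a little programming from dates already collected. The limitation is that such rates assume a roughly constant hazard. If events cluster early, a pooled rate understates toxicity in the longer-treated arm. The post-treatment part of the window may also include other anticancer therapy, since Protocol 5.4.2 prohibits none in that phase. The rates should therefore supplement the percentages and not replace them.
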